**Figure 10-1 Subdivision of ITT set for estimation of individual hazards for imputation**

**Step 1:**

According to the study protocol all subjects are to be followed until the end of the rivaroxaban/aspirin follow-up / end of the study and data on the primary efficacy outcomes are collected irrespective of whether or not a subject is on or off anti-thrombotic treatment. The cohort of subjects who prematurely discontinue any anti-thrombotic study treatment (i.e. either study

rivaroxaban bid and/or study aspirin treatment) will be used for imputation of unobserved follow-up time.

More specifically, for subjects who prematurely discontinued any anti-thrombotic study treatment, a Weibull survival model will be fitted to estimate the individual hazard of a primary outcome event at the last contact date of the rivaroxaban/aspirin portion of the trial. The model will be adjusted for treatment groups (rivaroxaban 2.5 mg bid + aspirin 100 mg od, rivaroxaban 5 mg bid + aspirin placebo od, rivaroxaban placebo + aspirin 100 mg od), stratification factor (not randomized to a proton pump inhibitor; pantoprazole 40 mg od; pantoprazole placebo) and the following baseline covariates:

- CAD and PAD, CAD only, PAD only
- Age (<65, 65 years or older)
- Region (North America, Western Europe, Eastern Europe, Asia Pacific and other, and South America)
- History of a prior heart failure
- History of prior stroke
- History of prior MI

The imputation model will also include a covariate indicating the occurrence of a major bleeding event (post-randomization event), if the bleeding occurred (start date) during the 90 days preceding the unrefuted primary efficacy outcome event or the censoring date relevant for primary analysis:

If the individual hazard for a subject cannot be estimated from the above model due to missing covariates the hazard estimate from a crude model – adjusted for treatment groups and stratification factor only – will be used for this subject (see Section 10.4.4).

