### Step 3:

To assess the robustness of the analyses for deviations from ignorable censoring the last step will be repeated after inflating the hazards for rivaroxaban/aspirin follow-up non-completers in the rivaroxaban groups. The hazards in the control group will not be inflated, that is, for these subjects, rivaroxaban/aspirin follow-up non-completion will be treated as ignorable. Thereafter, the multiple imputation described above will be repeated with the inflated hazards.

The inflation factor be increased stepwise to determine the factor F, for which the upper limit of the 95%-CI for the HR for rivaroxaban 2.5 mg bid + aspirin 100 mg od relative to rivaroxaban placebo + aspirin 100 mg od crosses 1 – the “tipping-point” – and the factor G, for which the upper limit of the 95%-CI for the HR for rivaroxaban 5 mg bid + aspirin placebo od relative to rivaroxaban placebo + aspirin 100 mg od crosses 1.

The following inflation factors will be considered: 10% to 200% increased by 10% steps, 200% to 500% increased by 50% steps and 500% to 1000% increased by 100% steps.

The sensitivity analysis described in this section will be repeated using a Weibull survival model fitted to all randomized subjects and adjusted for treatment groups, stratification factor and the baseline covariates described above.

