### 10.4.4 Parameter estimation

For subjects who prematurely discontinued any anti-thrombotic study treatment, a Weibull survival model will be fitted to estimate the hazard of a primary outcome event at the last contact date in the rivaroxaban/aspirin portion of the trial:

```
PROC LIFEREG DATA = <dataset> OUTEST=<dataset1>;
  MODEL ttevalue*ttecnsr(1) = trtgrp stratum <covariates> /
    DISTRIBUTION = weibull INTERCEPT=8 INITIAL=0.2;
  OUTPUT OUT=<dataset2> CDF=cdf XBETA=xbeta;
RUN;
/*
where
dataset = name of sub-dataset including all ITT subjects who prematurely
discontinued any anti-thrombotic study treatment
dataset1 = SAS data set containing the parameter estimates
dataset2 = SAS data set containing statistics (CDF and x'β) calculated after
fitting the model
ttevalue = time to first occurrence of primary efficacy outcome event
ttecnsr = censoring index (1 = right-censored, 0 = event)
trtgrp = variable coding randomized antithrombotic treatment group
        (0 = control group, 1 = rivaroxaban 2.5 mg + aspirin 100 mg)
stratum = variable for PPI stratification factor (three levels)
*/
```

The SAS LIFEREG procedure will be used to model the natural logarithm  $w = \log(t)$  of the survival time. The survival function used by SAS has the form

$$S(w) = \exp\left(-\exp\left(\frac{w-\mu}{\sigma}\right)\right),$$

where  $\mu$  is the location parameter and  $\sigma$  the scale parameter.

Re-parameterization by  $\lambda = \exp(\mu)$  and  $\beta = 1/\sigma$  results in the survival function  $S_1$  with

$$S(w) = S_1(t) = \exp\left(-\left(\frac{t}{\lambda}\right)^\beta\right).$$

The estimated hazard at the last contact date in the rivaroxaban/aspirin portion of the trial will be obtained from the fitted Weibull model, adjusted for treatment and baseline covariates for each subject.

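### The LIFEREG imputation code in SAP 10.4.4 does not implement the three-arm model of 10.4.3: the 5 mg arm has no code and there is no CLASS statement

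*SAP*

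**What the plan says.** Step 1 of Appendix 10.4.3 fits a Weibull model to subjects who stopped any antithrombotic study treatment early. "The model will be adjusted for treatment groups (rivaroxaban 2.5 mg bid + aspirin 100 mg od, rivaroxaban 5 mg bid" is how its list of groups begins; control is the third. The adjustment set also includes the PPI stratification factor (not randomized, pantoprazole, placebo), a five-level region, a three-level CAD/PAD grouping and several yes/no histories. Where covariates are missing, a crude model with treatment and stratum only takes over.

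Section 10.4.4 prints the code:

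- model line: "MODEL ttevalue*ttecnsr(1) = trtgrp stratum <covariates>", with no CLASS statement in the block;
- data set: "dataset = name of sub-dataset including all ITT subjects who prematurely" stopped any antithrombotic study drug, with no restriction by arm;
- treatment coding: "0 = control group, 1 = rivaroxaban 2.5 mg + aspirin 100 mg", and no further code;
- stratum: "stratum = variable for PPI stratification factor (three levels".

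Step 2 of 10.4.3 draws imputed events from the fitted hazards. Step 3 inflates those hazards in the rivaroxaban groups: "The inflation factor be increased stepwise to determine the factor F, for which the upper limit of the 95%-CI" reaches 1 for 2.5 mg plus aspirin, and G is the same quantity for 5 mg. Step 3 then repeats the exercise with a Weibull model fitted to all randomized subjects.

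**The concern.** The text describes nominal factors, and the code does not treat them as such. In LIFEREG a numeric variable that is not named in CLASS enters as a single slope. The two-code comment suits the pairwise Cox code elsewhere in the SAP. Here the data set spans three arms, and the third arm has no value.

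At stake is the base hazard for each arm in the missing-data analysis. It generates the imputed events, and F and G multiply it. If one arm has no hazard, its tipping point cannot be computed. If the hazard is pulled towards a straight line across arms, the reported robustness of each comparison shifts with it.

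**Working it through.** The SAP states no figure for this step, so none can be reproduced. The check sets text against code, then sizes one scenario.

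**Text against code**

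| Element | 10.4.3, Step 1 | 10.4.4 code |
|---|---|---|
| Arms in the data | three | three (all early discontinuers) |
| Treatment term | three named groups | one variable, codes 0 and 1 only |
| PPI factor | three unordered levels | one variable, not in CLASS |
| Region, CAD/PAD | five and three levels | inside a covariate placeholder |

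Possible ways to run the block:

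1. Codes as printed: 5 mg subjects have a missing treatment value and leave the fit. The crude fallback also needs treatment, so it does not rescue them. There are no 5 mg hazards and no G.
2. A third numeric code is added: arm and stratum become linear scores.
3. Character variables without CLASS: the procedure stops.

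None of these gives the model in 10.4.3.

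**Size under numeric coding.** Inputs: control incidence about 3.3% per year and a 20% relative risk reduction in both arms (SAP section 7). Assumed: codes 0 = control, 1 = 2.5 mg, 2 = 5 mg; equal exposure per arm; constant hazard (Weibull shape 1).

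The likelihood equations for fitted relative hazards a, ar, ar² are:

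- a(1 + r + r²) = 1 + 0.8 + 0.8 = 2.6
- a(r + 2r²) = 0.8 + 2 × 0.8 = 2.4

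So 2.8r² + 0.2r − 2.4 = 0, giving r = 0.891 and a = 0.969.

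| Arm | True, per 100 patient-years | Fitted | Fitted/true |
|---|---|---|---|
| Control | 3.30 | 3.20 | 0.969 |
| 2.5 mg + aspirin | 2.64 | 2.85 | 1.079 |
| 5 mg | 2.64 | 2.54 | 0.961 |

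Swapping codes 1 and 2 swaps the two rivaroxaban rows. Other assumed truths bracket this. With null effects, or hazard ratios of 0.90 and 0.81 (linear in the score), the arm error is zero. With 0.80 and 1.00, r = 1 and a = 2.8/3 = 0.933, so the 2.5 mg hazard is overstated by 0.933/0.80 − 1 = 17%.

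The PPI score adds to this. A Weibull fit to 600,000 simulated subjects used both scores, true hazard ratios of 0.80/0.80, stratum shares of 40/30/30% and an assumed hazard ratio of 1.3 for the non-randomized stratum. Cell hazards were off by about −9% to +18%.

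**Effect on F and G.** Assumed: half the planned events (826/2 = 413 control; 687/2 ≈ 344 per rivaroxaban arm), missing follow-up of 0.5% to 4% of subject-years, and between-imputation variance ignored. F is the extra inflation at which log(rate ratio) + 1.96 × √(1/d_C + 1/d_T) passes 0, where d counts observed plus expected imputed events.

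Example, 2% missing, categorical arms:

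- Control exposure is 413/0.033 = 12,515 years and rivaroxaban exposure is 344/0.0264 = 13,030 years. Missing time per arm is 0.02 × 12,515/0.98 = 255 years.
- At F = 4.60, d_C = 413 + 255 × 0.033 = 421.4 and d_T = 344 + 255 × 0.0264 × 5.60 = 381.8.
- The log rate ratio is −0.138 and 1.96 × SE is 0.138, so the limit is at 1.

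The SAP's grid is "10% to 200% increased by 10% steps, 200% to 500% increased by 50% steps and 500% to 1000% increased by 100% steps". Reading it as extra inflation, the first grid value at or above each result is in brackets.

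| Missing | F categorical → linear | G categorical → linear |
|---|---|---|
| 0.5% | 1815% → 1672% (both off the grid) | 1815% → 1890% (both off the grid) |
| 1% | 912% → 835% (1000 → 900) | 912% → 949% (1000 → 1000) |
| 2% | 460% → 416% (500 → 450) | 460% → 479% (500 → 500) |
| 4% | 234% → 206% (250 → 250) | 234% → 244% (250 → 250) |

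F falls by about 8% to 12% and G rises by about 4%. F moves by one grid value at most and G by none.

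**The case against.** The best defence is that 10.4.3 is the specification and is unambiguous, while the code is a skeleton with a covariate placeholder. A programmer following the text would use dummy variables or CLASS. The comment may be a pairwise template carried over from section 6.2.1.2, in which case treatment is binary and has no linearity problem.

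Part of this stands. The 0/1/2 coding is an assumption, and how region and CAD/PAD enter is not printed. The pairwise reading fits poorly, though. Section 10.4.6 restricts its data set to one rivaroxaban group and control, whereas 10.4.4 does not, and 10.4.3 describes one model with three groups. That reading would also leave the PPI stratum as a slope. Nor is omitting CLASS a house convention: the logistic code in section 5.4.2 of the separate pantoprazole SAP declares both its treatment and its stratum variable.

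A reader might infer that F and G are simply wrong, or wrong by several 10% steps. The documents do not support either. Distortion requires numeric scores and true effects that are not linear in them, and above 200% the grid moves in 50% and 100% steps.

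**Conclusion.** The mismatch between 10.4.3 and 10.4.4 is real, and no literal run of the printed block gives the specified model. The firm defect is that the 5 mg arm has no treatment code in a data set that contains it; the missing CLASS statement is the second. The consequence is conditional: no 5 mg hazards and no G if run as printed, or hazards that can be distorted if a third numeric code is supplied.

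Under 0/1/2 coding and the SAP's own 20% risk reduction in both arms, arm hazards are off by about −4% to +8%, and F and G move by about one grid step or less. That rests on equal exposure, half the planned events, 0.5% to 4% missing follow-up and an approximate tipping formula, none of which the SAP fixes.

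It would also be wrong to carry the point over to the main results. The primary stratified log-rank and Cox analyses do not use this code. The pairwise PHREG step in 10.4.6 has a 0/1 treatment and keeps the stratum in STRATA, so it needs no CLASS.

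**What to change.** In the LIFEREG block of 10.4.4, add a CLASS statement naming `trtgrp`, `stratum` and every multi-level covariate (region, CAD/PAD group). In the comment, define a code for each of the three arms. Apply the same to the crude fallback model and to the repeat fit in all randomized subjects. The cost is one line of code and one comment line; nothing else in the plan has to change.

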#### 10.4.5 Generation of random variables

Let the survival time  $T$  be Weibull distributed, with survival function  $S_1$ .

The conditional distribution function of  $T$  after the censoring date  $CD$  (given that no event was observed before) is given for  $s \geq 0$  by

$$\begin{aligned} G(s) := P(T \leq s + CD | T > CD) &= 1 - P(T > s + CD | T > CD) = 1 - \frac{P(T > s + CD)}{P(T > CD)} \\ &= 1 - \frac{S_1(s + CD)}{S_1(CD)}. \end{aligned}$$

With scale parameter  $\lambda$  and shape parameter  $\beta$  from the underlying Weibull distribution we have

$$G(s) = 1 - \frac{\exp\left(-\left(\frac{s + CD}{\lambda}\right)^\beta\right)}{\exp\left(-\left(\frac{CD}{\lambda}\right)^\beta\right)},$$

hence

$$G^{-1}(s) = \lambda \left( \left( \frac{CD}{\lambda} \right)^\beta - \log(1 - s) \right)^{1/\beta} - CD.$$

If  $s$  is generated as a random variable with uniform distribution between 0 and 1, a random variable with distribution function  $G$  can be generated using the inverse transformation technique from

$$\lambda \left( (CD/\lambda)^\beta - \log(1 - \text{rand}('uniform')) \right)^{1/\beta} - CD.$$

#### 10.4.6 Analysis of imputed data sets

SAS program code corresponding to the following will be used to get a dataset with hazard ratio estimates from the 1,000 datasets with imputed primary outcome events:

```
ODS LISTING CLOSE;
PROC PHREG DATA = <dataset>;
  MODEL ttevalue * ttecnsr(1) = trtgrp / RL TIES=EFRON ALPHA=0.05;
  STRATA stratumn;
  ODS OUTPUT PARAMETERESTIMATES=phregparms;
  BY _imputation_;
RUN;
ODS LISTING;
/*
where
dataset = name of sub-dataset including all ITT subjects randomized to
          respective rivaroxaban treatment group and control group
trtgrp   = variable coding randomized antithrombotic treatment group
          (0 = control group, 1 = rivaroxaban 2.5 mg + aspirin 100 mg)
ttevalue = time to first occurrence of primary efficacy outcome event
ttecnsr  = censoring index (1 = right-censored, 0 = event)
stratumn = variable for PPI stratification factor (three levels)
_imputation_ = variable for the imputation
*/
```

Finally, the results from the 1000 complete datasets will be combined to produce inferential results using the following program code:

```
PROC MIANALYZE PARMS=phregparms;
  MODELEFFECTS trtgrp;
RUN;
```

**A randomized controlled trial of rivaroxaban for the prevention of major cardiovascular events in patients with coronary or peripheral artery disease (COMPASS - Cardiovascular Outcomes for People using Anticoagulation Strategies)**

## Abbreviations

AE	Adverse event
ALI	Acute Limb Ischemia
AUS/ISR/ZAF	Australia/Israel/South Africa
bid	Twice daily
CAD	Coronary artery disease
CDB	Clean database
CHD	Coronary heart disease
CI	Confidence interval
CLI	Chronic Limb Ischemia
COMPASS	Cardiovascular Outcomes for People using Anticoagulation Strategies
COMPASS LTOLE	COMPASS Long-term Open-Label Extension
CRF	Case report form (either paper or electronic)
CSR	Clinical study report
CV	Cardiovascular
DSMB	Data Safety Monitoring Board
eGFR	estimated glomerular filtration rate
GI	Gastrointestinal
Hb	Hemoglobin
ICH	International Conference on Harmonization
ISTH	International Society on Thrombosis and Haemostasis
ITT	Intention-to-treat
MI	Myocardial infarction
NSAID	Non-steroidal anti-inflammatory drugs
od	Once daily
PAD	Peripheral artery disease
PPD	
PPI	Proton pump inhibitor
SAE	Serious adverse event
SAP	Statistical analysis plan
SAS	Statistical Analysis Software

## 1. Introduction

On February 06, 2017 the Data Safety Monitoring Board (DSMB) for the COMPASS study recommended that the antithrombotic study treatment arms rivaroxaban 2.5 mg bid/aspirin 100 mg od, rivaroxaban 5 mg bid, and aspirin 100 mg od be stopped as soon as an orderly close-out of this portion of the COMPASS trial could be carried out based on results of the first formal interim analysis. The DSMB made no recommendations regarding early termination of the pantoprazole treatment arms of the study. The Steering Committee decided that the pantoprazole study treatment arms will continue.

The database (Clean Database 1, CDB1) underlying the CSR and the publications is based on a cut-off date of July 22, 2017 and, at Bayer, the release date of the first clinical database on August 04, 2017. The results for the antithrombotic randomization have been analyzed and reported in the clinical study report (CSR, PH-39342) of the COMPASS study and multiple scientific publications. The statistical analyses comprise records up to the subjects' rivaroxaban/aspirin washout visits since these data are considered relevant to the antithrombotic study treatment arms.

The close-out of the pantoprazole treatment arms will lead to a second database release (Clean Database 2, CDB2). The primary purpose of the analyses described in this SAP is the

evaluation of outcomes with respect to the pantoprazole randomization. All outcomes with respect to the antithrombotic randomization have been evaluated extensively at CDB1. In addition, it will be explored whether PPI treatment interferes with the effects of rivaroxaban.

Hence, this SAP is to be read in conjunction with the study protocol and the [SAP](#), version 4.1, of the COMPASS study. The SAP describes the planned statistical analyses after CDB2 in the COMPASS study, focusing on analyses with respect to the pantoprazole/placebo randomization.

## 2. Study Objectives

The main objective for the pantoprazole randomization is

- To determine whether pantoprazole 40 mg od compared with placebo reduces the risk of upper gastrointestinal bleeding, ulceration, or gastrointestinal obstruction or perforation in subjects with CAD or PAD receiving antithrombotic medications.

Other objectives for the pantoprazole randomization are:

- To determine the effect of pantoprazole 40 mg od compared with placebo on the risk of pneumonia, clostridium difficile (C. diff) and other enteric infections, bone fractures, and new diagnosis since randomization of gastric atrophy, chronic kidney disease, diabetes, chronic obstructive lung disease and dementia in subjects with CAD or PAD.
- To determine whether treatment with pantoprazole 40 mg od potentially modifies the effects of antithrombotic treatment on major cardiovascular outcomes or bleeding events. I.e. whether pantoprazole interacts with the treatment effects of rivaroxaban 2.5 mg bid/aspirin 100 mg od vs. aspirin 100 mg od in its impact on outcomes.
- To determine whether treatment with pantoprazole 40 mg od has an effect on premature discontinuation of antithrombotic study treatment.

For further details on study objectives, please refer to integrated [SAP](#), version 4.1.

## 3. Study Design

For the general study design, please refer to integrated SAP, version 4.1.

[figure not shown]
Following the decision of early termination of the antithrombotic treatment arms, all subjects were to stop randomized antithrombotic study treatment with the Final rivaroxaban/aspirin Follow-up Visit (in mid 2017).

- Subjects *randomized to pantoprazole or pantoprazole placebo* were to continue study follow-up as per study protocol up until their Final pantoprazole/placebo Follow-Up Visit (planned for mid 2018).
- Subjects *not randomized to pantoprazole or pantoprazole placebo* were followed-up until their Rivaroxaban/aspirin Washout Visit, i.e. the end of the rivaroxaban/aspirin portion of the trial.

All subjects from COMPASS trial are to be invited to join the COMPASS Long-term Open-Label Extension (COMPASS LTOLE) as long as they continue to meet the COMPASS eligibility criteria plus specific criteria for LTOLE as described in the integrated study

protocol, version 4.0. Initiation visits for the LTOLE study started early 2018 and occur dependent on the approval of the integrated study protocol in the respective country.

Continued antithrombotic therapy between the Final rivaroxaban/aspirin Follow-up Visit and the LTOLE initiation visit was at the discretion of the investigator.

## 4. General Statistical Considerations

Please also refer to integrated SAP, version 4.1.

### 4.1 Analysis Sets

The following analysis sets will be used for the analysis of the data from CDB2.

- **Intention-to-treat Analysis Set (ITT):**  
The intention-to-treat analysis set, also termed full analysis set in the International Conference on Harmonization (ICH) E9 guideline, includes all subjects randomized to antithrombotic study treatment. The ITT set comprises both subjects randomized to pantoprazole/placebo and subjects not randomized to pantoprazole/placebo.
- **Pantoprazole ITT Analysis Set (pantoprazole ITT):**  
The pantoprazole ITT analysis set comprises all subjects that have been randomized to pantoprazole 40mg or pantoprazole placebo.
- **Pantoprazole Safety Analysis Set (pantoprazole SAF):**  
The safety analysis set for secondary analyses related to the pantoprazole randomization (pantoprazole safety analysis set) will include all subjects randomized to pantoprazole/placebo who received at least one dose of randomized pantoprazole/placebo medication.  
A subject is considered to have taken at least one dose of pantoprazole/placebo study

medication if the date of permanent discontinuation of pantoprazole/placebo study treatment is later than the randomization date.

[figure not shown]
